6.2.6 Sub-study Analysis Set (SSA)

6.2.6.1 Clinical Laboratory Sub-study Analysis Set (SSA 1)

All subjects in the All Enrolled Set who actually receive at least one dose of study vaccination and participated in the clinical laboratory sub-study.

6.2.6.2 Sub-study Analysis Set for Cell-mediated Immunity directed against HBs (SSA 2)

All subjects in the All Enrolled Set who actually receive at least one dose of study vaccination and participated in optional sub-study of cell-mediated immunity directed against HBs.

6.2.7 Sub-groups

The following key sub-groups of interest will be pre-specified:

- Age group: (18 44 years old vs 45 64 years old vs >= 65 years old)
- Age category: (18 39 years old vs 40 49 years old vs 50 59 years old vs 60 69 years old vs >= 70 years old)
- Gender (male vs female)
- BMI ($\leq 30 \text{ vs} > 30$)
- Smoking Status (current vs past vs non-smoker)

Statistical Analysis Plan

- Diabetes (Diabetic vs non-diabetic)
- Daily alcohol consumption (≥ 4 drinks/day vs 2-3 drinks/day vs 0-1 drink/day)
- Non-study licensed vaccines (no vaccination vs vaccination): Any concomitant vaccines received during the study
- Race (White vs Black or African American vs Other)
- Ethnicity (Hispanic or Latino vs Non Hispanic or Latino)
- Country/region (United States vs Canada vs Europe)

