6.3.1 Screening

The screening will be conducted within 28 days (4 weeks) of Visit 1. After obtaining informed consent in accordance with ICH GCPs, inclusion/exclusion criteria will be assessed and the following data/samples will be obtained:

- Medical History/ Demographics
- Physical Examination (or at Visit 1 prior to injection)
- Height and weight
- Concomitant medications
- Urine Pregnancy test (in females of childbearing potential)
- Blood sampling for screening hematology, blood chemistry and serology tests (HIV, Hepatitis C and B)
- Urinalysis

If the subject is eligible, the study staff will proceed to complete the enrollment procedures and to schedule the first vaccination visit. Study subjects will be requested not have any inactivated vaccines (e.g. influenza) 2 weeks prior to 2 weeks after each study vaccination and not to have attenuated vaccines (e.g. MMR) 4 weeks prior to 4 weeks after each study vaccination.

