6.3.7 End of study visit

The end of study visit will be performed on Study Day 336 (+/-14 days) or earlier in case of withdrawal.

- Physical/History-directed physical examination.
- Blood samples for measurement of anti-HBs, anti pre-S1, and anti pre-S2 levels and characteristics will be taken.
- SAE, AE requiring medical attention and the use of concomitant medications will be recorded in the eCRF
- In case of withdrawal: reason for withdrawal will be documented in the eCRF
- Subject will be advised that the study center staff may need to contact them in case new information, such as lack of seroprotection (anti-HBs levels <10 mIU/mL), becomes available.

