9.3.7 Sub Groups

The following key sub-groups of interest will be pre-specified:

- Gender (male vs female)
- BMI (<= 30 vs > 30)
- Smoking Status (current vs past or non-smoker)
- Age cohort (18-44 years, 45-64 years, ≥65 years)
- Diabetes (Diabetic vs non-diabetic)
- Daily alcohol consumption (≥ 4 drinks/day vs 2-3 drinks/day vs 0-1 drink/day)
- Non-study licensed vaccines (no vaccination vs vaccination)
- Race and Ethnicity

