- **Emergence during vaccination phase**: start date on or after the first date of injection of study vaccine or, adverse event increase in severity including to "serious" adverse event.

If an adverse event start date is equal to the first date of vaccination injection, missing or unknown, the adverse event will be considered as emergent.

When start and/or end dates of an adverse event are only partially known, adverse events will be categorized as emergent before, during (or after) vaccination phase using the following rules:

• If the partial end date is before (<) the first study vaccination (i.e., year or year & month is/are before the first study vaccination year or year & month) then the adverse event is emergent before vaccination phase.

Statistical Analysis Plan

If the partial start date is equal or after (≥) the first study vaccination (i.e., year or year & month is/are after or the same as the first study injection year or year & month) then the adverse event is emergent during vaccination phase.

The **maximum event severity** is the greatest severity associated with a preferred term for a reported adverse event according to the following order: Mild < Moderate < Severe < Potentially life threatening. Unknown/ Missing severity is considered as potentially life threatening.

Multiple AEs with the same PT for the same subject are counted only once.

Vaccination-related Adverse Events are those for which the cause has been evaluated by the investigator, and recorded either as very likely/certain, possibly related, probably related or unknown/missing.

Pre-Study, Concomitant and Post-Study Medications

A **pre-study medication** is a medication used only before the first study vaccination (i.e. medication end date < first study vaccination date).

A **post-study medication** is a medication used only after study termination (i.e. medication start date > study termination date). This will not be collected in the clinical database and will not be reported in the CSR.

All other medications are **concomitant**.

When start and/or end dates of a medication intake are missing, the medication is considered as concomitant with the study vaccination schedule.

If the first study vaccination date is missing then the medication is considered as concomitant with the study vaccination schedule, provided that the study vaccine was administered to the subject.

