where seroprotection represent the seropositive event, trt represents treatment group and agegrp represents age group (18 - 44 years, 45 - 64 years, >=65 years).

The estimated proportion of responders (i.e., estimated responder rate) and the difference in the proportion of responders between Sci-B-VacTM and Engerix-B® will be estimated, as well as the 2-sided 95% CIs for the difference. The creation of the estimates of the proportions and difference in proportions will be completed using the process detailed below:

Statistical Analysis Plan

- 1. Use the logistic regression model to calculate:
 - a) Least squares mean estimates of the log odds of Sci-B-VacTM (Gc) and Engerix-B® (Gp), as well as their corresponding standard errors (S_C and S_P, respectively)
 - b) Standard error of the least squares mean estimate of the log odds ratio (S_R)
- 2. Compute estimates for predicted proportions using the following transformations:

$$P_C = \exp(G_C)/(1 + \exp(G_C))$$
$$P_P = \exp(G_P)/(1 + \exp(G_P))$$

The difference in proportions is then given by:

$$D = P_C - P_P$$

3. Estimate the standard error of D by:

$$S_D = sqrt[P_C^2 (1-P_C)^2 S_C^2 + P_P^2 (1-P_P)^2 S_P^2 + P_C (1-P_C) P_P (1-P_P) S_R^2 - P_C (1-P_C) P_P (1-P_P) (S_C^2 + S_P^2)]$$

Analyses of the co-primary endpoints will also be conducted and reported by key sub-groups using the sub-groups identified in Section 6.2.7.

• Sample SAS code for the subgroup analysis of binary data:

```
PROC FREQ; * specify and sub-select data set as applicable;

TABLES subgroup*trt*seroprotection/riskdiff (cl=mn); * numerical 0/1-scores identify 'event';
RUN;
```

where seroprotection represent the seropositive event, trt represents treatment group and subgroup represents subgroup defined in Section 6.2.7.

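### The non-study vaccine subgroup counts vaccines given after the serology being analysed, which may dilute any heterogeneity at Day 196 and does so most at Days 28 and 56

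*SAP*

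**What the plan says.** Protocol 9.3.7 lists the subgroup as "Non-study licensed vaccines (no vaccination vs vaccination" and gives no time window. SAP 6.2.7 adds one: "Non-study licensed vaccines (no vaccination vs vaccination): Any concomitant vaccines received during the study".

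SAP 6.1.1 shows how far that window reaches. A post-study medication "is a medication used only after study termination (i.e. medication start date > study termination date", a pre-study medication is one that ended before the first study dose, and "All other medications are concomitant". On missing dates it says: "When start and/or end dates of a medication intake are missing, the medication is considered as concomitant with the study vaccination schedule". Protocol 6.1.9 has other vaccines recorded as concomitant medication, and Protocol 6.3.7 still collects concomitant medication at the final visit: "The end of study visit will be performed on Study Day 336 (+/-14 days) or earlier in case of withdrawal".

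SAP 6.3.13.2 applies the subgroup list to the main result at Day 196: "Analyses of the co-primary endpoints will also be conducted and reported by key sub-groups using the" list in 6.2.7. SAP 6.3.13.3 applies it to the secondary comparisons (Sci-B-Vac at Day 56 or 168 against Engerix-B at Day 196). SAP 6.3.13.4 applies it to the exploratory endpoints by visit.

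Protocol 6.3.1 asks subjects to avoid inactivated vaccines "2 weeks prior to 2 weeks after each study vaccination", and attenuated vaccines for 4 weeks on either side.

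**The concern.** The response is fixed when the serum is drawn, but exposure goes on accumulating until study end. A subject whose only other vaccine is given on Day 250 enters the vaccination stratum for a sample taken 54 days earlier. That stratum then mixes subjects exposed before the sample with subjects not yet exposed, and no other section of either document limits the date.

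What is at stake is the interpretation of one listed subgroup. If other vaccines did change the difference between Sci-B-Vac and Engerix-B, the two strata would look more alike than they should. Similar results in both strata would then be hard to read as reassurance.

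**Working it through.** The documents give no figure for this point, so there is nothing to reproduce. The inputs are study days: doses on Days 0, 28 and 168; samples on Days 28, 56, 168, 196 and 336; study end on Day 336 (SAP 6.1 and Protocol 6.3).

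**Step 1: permitted days for another vaccine, at nominal visit days.**
- Inactivated, more than 14 days from every dose: Days 43–153 (111 days) and 183–336 (154 days), 265 in total.
- Attenuated, more than 28 days from every dose: Days 57–139 (83 days) and 197–336 (140 days), 223 in total.

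**Step 2: share of days that fall after each sample.**

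| Sample | All days (of 336) | Permitted, inactivated (of 265) | Permitted, attenuated (of 223) |
|---|---|---|---|
| Day 28 | 308 (92%) | 265 (100%) | 223 (100%) |
| Day 56 | 280 (83%) | 97 + 154 = 251 (95%) | 223 (100%) |
| Day 168 | 168 (50%) | 154 (58%) | 140 (63%) |
| Day 196 | 140 (42%) | 140 (53%) | 140 (63%) |
| Day 336 | 0 | 0 | 0 |

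These are shares of calendar time. They become shares of subjects only on three assumptions: uniform timing, one vaccine per subject and, for the last two columns, full respect of the spacing windows. A subject vaccinated both before and after the sample is classed correctly. With two independent, uniformly timed inactivated vaccines per subject, the late-only share at Day 196 would be 0.528² = 0.28.

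**Step 3: effect on the quantity the SAP estimates.** The SPR subgroup code in SAP 6.3.13.2 gives Sci-B-Vac minus Engerix-B within each stratum. Let D_E be that difference in subjects exposed before the sample, D_U the difference in those not exposed, and s the share of the vaccination stratum exposed only afterwards. Assume s is the same in both arms and that late vaccinees respond like the unvaccinated. Then:

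- vaccination stratum: (1 − s)·D_E + s·D_U
- no-vaccination stratum: D_U
- observed gap between strata: (1 − s)·(D_E − D_U)

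For an illustrative true gap of 10 points (an assumption, not a figure from the plan):

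| s | Observed gap (points) |
|---|---|
| 0.10 | 9.0 |
| 0.25 | 7.5 |
| 0.417 | 5.8 |
| 0.528 | 4.7 |
| 0.628 | 3.7 |
| 0.90 | 1.0 |

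**Step 4: secondary comparisons.** The arms are sampled on different days. Cutting exposure at each arm's own sample would, for inactivated vaccines, leave 14 permitted days (Days 43–56) for Sci-B-Vac at Day 56, against 111 + 14 = 125 (Days 43–153 and 183–196) for Engerix-B at Day 196. Subgroup membership would then depend on arm, so a sample-specific cut-off cannot simply be carried over to these analyses.

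**The case against.** The strongest reply is that this is one of eleven subgroups, with no alpha, no success criterion and no specified interaction test for SPR. Subgroup comparison is already an exploratory objective (SAP 1.3). Vaccine dates are in the eCRF, so a restricted re-analysis remains possible later. All of that stands, and it limits the importance of the point.

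Four stronger readings are tempting, and the documents do not support them.

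- *The subgroup can show nothing about other vaccines.* Subjects exposed before the sample remain in the vaccination stratum. At Day 196 the gap is diluted, not removed, and a difference could still appear.
- *More than half of the vaccination stratum is misclassified.* The 53% depends on the assumptions in step 2. Protocol 6.1.9 does not require withdrawal for a vaccine inside the windows and says only that it may affect per-protocol evaluability. The superiority analysis uses the FAS, which keeps such subjects, and vaccines given close to a study dose nearly all precede Day 196. The real share is not known.
- *The SAP compares vaccinated with unvaccinated subjects on SPR.* It estimates the treatment difference within each stratum. Dilution matters for heterogeneity between those differences.
- *Drop-out after Day 196 worsens the error.* A subject who leaves after Day 196 with no earlier vaccine stays in the no-vaccination stratum, which is the correct class for that endpoint.

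**Conclusion.** The point holds as a defect in a subgroup definition. As written, SAP 6.2.7 classes subjects first vaccinated after the serology as exposed, and nothing elsewhere corrects it. At Day 196 this may dilute any heterogeneity in the treatment difference by a factor of (1 − s), with s unknown. Calendar time gives 42%, and 53% or 63% under uniform timing with the windows respected; the plausible range is wide.

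The dilution is greatest at Day 28, where no permitted day precedes the sample, and at Day 56, where 14 of 265 permitted inactivated-vaccine days and no attenuated-vaccine days do. At Day 336 the definition fits. The missing-date rule in SAP 6.1.1, if carried into the subgroup, adds further subjects whose exposure may not precede the sample.

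The co-primary tests, their populations, alpha and power are untouched. The change is worth making because it is cheap and the classification error is plain, not because any main conclusion depends on it.

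**What to change.** Amend SAP 6.2.7 before unblinding:

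- **Co-primary and same-day exploratory analyses:** exposure means a non-study vaccine dated after the first study dose and before the serum sample at that time point. Subjects vaccinated only later go into the no-vaccination stratum. At Day 336 this broadly reproduces the present definition.
- **Secondary comparisons:** use one cut-off in both arms, for example before Day 56 for the Day 56 comparison and before Day 168 for the Day 168 comparison, so that membership does not depend on arm.
- **Missing vaccine dates:** state an explicit rule for this subgroup and do not inherit the default in SAP 6.1.1 without comment.
- **Reporting:** describe the subgroup as post-randomisation and descriptive. A date cut-off does not make receipt of another vaccine a randomised or baseline factor.

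The cost is a short SAP paragraph and date comparisons on data already collected. The vaccination stratum becomes smaller and its intervals wider, with few or no exposed subjects at Days 28 and 56, where the SAP could say that the subgroup will not be reported if it is empty. With a common early cut-off, Engerix-B subjects vaccinated between the cut-off and Day 196 stay in the no-vaccination stratum. That is the price of treating the arms alike, and it should be stated.

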6.3 Statistical Analysis Methods

6.3.1 Listings and Descriptive Statistics

All original and derived parameters as well as population characteristics will be listed and described using summary statistics. Frequency counts (number of subjects [n] and percentages) will be made for each qualitative variable. Descriptive statistics (n, mean, standard deviation [SD], median, minimum and maximum) will be calculated for each quantitative variable (unless otherwise stated). All listings will include repeated and unscheduled measurements.

All descriptive statistics will be presented by treatment group and visit. The baseline for all measurements (where applicable) will be the last pre-vaccination measurement. Descriptive statistics for all data obtained at Screening and follow-up will be presented separately.

6.3.2 Statistical Significance Level

All statistical tests will be two-sided and will be performed at the 5% level of significance, unless otherwise stated.

6.3.3 Software

All statistical analyses will be performed using Statistical Analysis Software (SAS®) Version 9.3 or later.

6.3.4 Study Visits

Laboratory data, vital sign data and physical examination data will be summarized or listed using the scheduled visits (See Table 1).

Table 1: Study Visits and Analysis Visits

Nominal Study Visit	Analysis Visit	Target Study Day*
---------------------	----------------	-------------------

Statistical Analysis Plan

Screening	Screening	-28
Visit 1	Day 0	1
Visit A1	Day 7	8
Visit 2	Day 28	29
Visit A2	Day 35	36
Visit 3	Day 56	57
Visit 4	Day 168	169
Visit A3	Day 175	176
Visit 5	Day 196	197
Visit 6	Day 336	337
Unscheduled	Unscheduled	

^{*} Study Day 1 is the date of first vaccination is administered to the subject. Study Day = (date of event/visit – first vaccination date) if it is before the first vaccination. Study Day = (date of event/visit – first vaccination date) + 1 if it is on or after the first vaccination.

Unscheduled assessments will be included in listings, but not in summaries. If a subject has multiple assessments within the same post-baseline analysis visit, the following rules will be established to select the data to be included in the descriptive summary:

- If multiple assessments occur within a given analysis visit, the assessment closet to the target study day will be used for analysis purposes.
- If there are 2 or more values equal distance to the target study day, then the last assessment, within the analysis visit, will be used in the analysis.

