3.3 Secondary endpoints

- SPR on Study Days, 56 and 168, 4 weeks and 20 weeks after receiving the second Sci-B-Vac[™] vaccination (just prior to receiving the third vaccination), and the SPR on Study Day 196, 4 weeks after receiving the third Engerix-B[®] vaccination
- Number (%) of subjects-reported, solicited (on the day of vaccination and during the next 6 days), unsolicited AE (on the day of vaccination and during the next 27 days), and number of Serious SAEs, medically significant events (condition prompting emergency room visit, physician visit not related to a common disease/not a routine visit or an SAE not related to a common disease) or new onset of chronic illness through Study Day 336. Adverse events will be classified by Medical Dictionary for Regulatory Activities (MedDRA) system organ class and preferred term, severity, seriousness, investigator and Sponsor causality assessment, and time since vaccination.
- Number (%) of subjects with abnormal vital signs, and/or physical examination findings compared to baseline.

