6.1.6 Vital signs

Oral temperature, blood pressure (systolic/diastolic), heart rate, and respiratory rate will be assessed at baseline and at each vaccination visit and recorded in the eCRF. Any abnormal vital sign after injection should be reassessed.

The oral body temperature of all subjects will be measured prior to any study product administration. The subject should be instructed to refrain from eating or drinking 30 minutes prior to obtaining the temperature. If the subject has a fever (defined as temperature ≥38.0°C/100.4°F oral) on the day of injection, the vaccination visit will be rescheduled within the allowed interval for the visit.

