6.2.4 Sub-Studies

6.2.4.1 Clinical laboratory sub-study

At select study sites, clinical laboratory parameters (hematology, biochemistry) will be assessed one week after each vaccination with either Sci-B-Vac or Engerix-B® and compared to baseline (pre-vaccination) values, as part of a clinical laboratory sub-study. All subjects enrolled at these select sites will be required to come for three additional visits and to provide four additional blood samples, beyond those required for the main study. The clinical laboratory sub-study will include at least 10% of all subjects enrolled to the entire trial.

Blood samples for the clinical laboratory sub-study will be collected at baseline (Day 0, Visit 1) prior to receiving any study vaccine, and at each of the three additional visits (additional visits A1, A2 and A3 in Appendix 2 Schedule of Events), to be scheduled 1 week after each vaccination with Sci-B-Vac™ or Engerix-B® on Study Day 7 (-3/+7 days), Study Day 35 (-3/+7 days) and Study Day 175 (-3/+7 days), respectively. The following clinical laboratory parameters will be evaluated:

Hematology

- o White blood cell count with differential
- o Red blood cell count
- Hematocrit (HCT)

- Mean cell hemoglobin (MCH)
- Mean cell hemoglobin concentration (MCHC)
- Mean corpuscular volume (MCV)
- o Hemoglobin
- o Platelet count
- Biochemistry:
 - o Blood urea nitrogen (BUN), serum creatinine.
 - Alkaline phosphatase (AP), alanine transaminase (ALT), aspartate transaminase (AST), total and conjugated bilirubin, gamma-glutamyl-transferase (GGT)

Safety laboratory evaluations may be repeated if indicated (e.g. follow-up of a clinically significant laboratory abnormality (from baseline assessment))

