6.3.14.5 Vital Signs

Vital signs data will be listed by subject including changes from baseline. The baseline for the vital signs measurements will be the latest non-missing results obtained before first vaccine injection.

All vital sign data will be summarized using descriptive statistics. Summaries will be provided for the observed values and changes from baseline at each scheduled visit. In addition, absolute and change from baseline values will be categorized according to the toxicity scales (See protocol Appendix 3 for vital signs) and summarized by time point using shift tables.

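### The one-value-per-visit rule in SAP 6.3.4 can equal or understate, never exceed, the worst post-dose grade in the vital-sign and laboratory toxicity tables

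*SAP*

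**What the plan says.** **Selection rule.** SAP 6.3.4 covers laboratory, vital-sign and physical-examination data. It opens its rule with "If a subject has multiple assessments within the same post-baseline analysis visit" and keeps the value closest to the target study day. For values equally distant from that day, the text continues: "then the last assessment, within the analysis visit, will be used in the analysis". Just before this it states: "Unscheduled assessments will be included in listings, but not in summaries". Study day is a difference of calendar dates, with no clock time.

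**When readings are taken.** Footnote (d) of the schedule in SAP 6.1 gives two vital-sign readings per vaccination, one before and one 30 minutes after. Protocol 6.1.6 adds: "Any abnormal vital sign after injection should be reassessed". Protocol 6.3.2 repeats this for the vaccination visits. For the laboratory sub-study, Protocol 6.2.4.1 says: "Safety laboratory evaluations may be repeated if indicated".

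**Where the values go.** For vital signs, SAP 6.3.14.5 says that "absolute and change from baseline values will be categorized according to the toxicity scales" and shown in shift tables by time point. SAP 6.3.14.4 does the same for laboratory values.

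**Endpoints served.** Protocol 3.3 lists as a secondary endpoint: "Number (%) of subjects with abnormal vital signs, and/or physical examination findings compared to baseline". Protocol 3.4 lists the number of subjects with abnormal laboratory parameters as an exploratory endpoint of the sub-study.

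**The concern.** A closest-then-last rule is neutral when extra readings arise for reasons unrelated to the result. Here the extra reading exists because the previous one was abnormal, so choosing the later reading is selection on the outcome. The rule also does not separate readings before the injection from readings after it.

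The tables concerned are meant to show how many subjects became abnormal after vaccination. If the value carried into them can be the reading after recovery, or cannot be a worse reading taken outside the schedule, any departure from the worst post-dose grade is downward. The vital-sign tables serve a secondary safety endpoint and the laboratory tables serve the sub-study endpoint.

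**Working it through.** The plan states no figure to reproduce. The check applies the rule to assumed readings.

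**Inputs from the documents.** Study day = visit date − first vaccination date + 1. The V2 target is study day 29 (SAP 6.3.4, Table 1). Systolic grades are 141–150 Grade 1, 151–155 Grade 2 and above 155 Grade 3 (SAP 6.3.14.2).

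**Assumed V2 readings.** 138 pre-dose, 158 at 30 minutes (Grade 3) and 139 on re-check (ungraded).

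**Step 1: do the readings tie?**

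| Days after first dose | Study day | Distance from 29, all three readings |
|---|---|---|
| 25 | 26 | 3 |
| 28 | 29 | 0 |
| 35 | 36 | 7 |

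Readings on one date always tie, so the last one is taken.

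**Step 2: which reading is kept?**

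| Label of the re-check | Readings that tie | Kept | Grade tabulated | Worst post-dose grade |
|---|---|---|---|---|
| Nominal visit | 138, 158, 139 | 139 | none | 3 |
| Unscheduled | 138, 158 | 158 | 3 | 3 |

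The results are the same on all three days, and also if only post-injection readings are compared.

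**Step 3: a re-check that is worse.** Assume 151 at 30 minutes (Grade 2) and 158 on re-check (Grade 3). Stored under the nominal visit, 158 is kept and the table shows Grade 3. Coded unscheduled, 151 is kept and the table shows Grade 2.

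**Step 4: direction.** Where a post-dose reading exists, the value kept is one of the post-dose readings, so its grade cannot exceed the worst of them. Each label has a case in which the grade is understated (Step 2, first row; Step 3). Under both labels the pre-dose 138 is dropped. A subject with no post-dose reading would contribute the pre-dose value to the same visit row.

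**Step 5: laboratory values.** The A1 target is study day 8, and the window of Day 7 −3/+7 days runs from study day 5 to study day 15.
- First draw on study day 5: distance 8 − 5 = 3. A repeat coded to A1 on study days 5 to 11 is at distance 3 or less, so it is nearer or ties as the later value, and it replaces the first.
- First draw on study day 8: distance 0. Only a same-date repeat displaces it.
- First draw after study day 8: a later repeat is further away, so again only a same-date repeat displaces it.
- Repeat coded unscheduled: the first value stays, and a worse repeat is only listed.

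**Size.** The documents give no rate of abnormal readings, re-checks or normalisation. Purely as an illustration under the nominal-visit label: if a share p of subjects is abnormal at 30 minutes and a share q of those normalise on re-check, the table shows p(1 − q). With p = 10% and q = 50% to 80%, that is 5% to 2%. Both p and q are assumptions.

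**The case against.** **The label is open.** The re-check is not one of the two scheduled readings. If it is coded unscheduled, the abnormal 30-minute value stays in the table. This stands: neither document fixes the label. Some text leans towards the nominal visit. Table 1 lists Unscheduled as a type of visit, and SAP 6.3.1 names repeated measurements apart from unscheduled ones. That does not settle it. The unscheduled label also leaves the other loss, shown in Step 3.

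**Abnormal vital signs are counted elsewhere.** SAP 6.3.14.2 treats 0–30 minute heart rate, blood pressure and respiratory rate abnormalities as solicited events, tabulated by severity after each vaccination. The visit rule is not written for those tables, and listings keep every repeated and unscheduled value. This stands as partial mitigation. The SAP does not say which 0–30 minute reading is graded for those tables; the maximum-severity rule in SAP 6.1.1 sits under unsolicited events. The endpoint in Protocol 3.3 is a comparison with baseline, which the shift tables provide.

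**Laboratory repeats are optional and most naturally unscheduled.** This stands, so replacement there needs the coding and timing in Step 5. There is, however, no solicited-event route for laboratory values. Under Protocol 7.1.5 an abnormal result becomes an AE only if it meets the criteria for clinical significance.

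**Scope.** The rule is limited to post-baseline visits, so it clearly reaches V2 and V4; its use on post-dose readings at V1 is unclear. It is framed for the descriptive summary. Its use in the shift tables is an inference, supported by its reference to analysis purposes. Shift tables by time point could be built with separate pre-dose and post-dose rows, but the SAP does not define them.

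**A confirmatory reading is a legitimate display.** This is true for by-visit means. It is less suitable for a count of subjects with an abnormality.

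**Conclusion.** The point holds in a limited form. At V2 and V4, and in narrower circumstances for laboratory values, the rule as written yields a tabulated grade that equals or falls below the worst post-dose grade, whichever way the re-check is labelled. Read literally, it also discards the pre-dose reading at those visits. This rests on the rule applying to the shift tables, which is inferred, and on a post-dose reading being present.

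A reader might go further and infer that re-checks will certainly erase abnormal readings from the safety reporting. The documents do not support that: the label is undefined, the solicited-event tables are separate, and all values are listed. Nor do they support a claim that a difference between the vaccines would be hidden. No rates are given. With equal q in both arms, p(1 − q) shrinks the absolute difference but leaves the ratio unchanged. Safety is analysed descriptively, with no hypothesis tests (Protocol 9.8). What is established is the direction of the possible error, not its size.

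**What to change.** Amend the SAP before unblinding:

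- **6.3.4:** limit the closest/last rule to descriptive summaries of continuous values.
- **6.3.4 and 6.3.14.5:** define pre-dose and post-dose as separate time points at each vaccination visit, V1 included.
- **6.3.4:** state whether a re-check or laboratory repeat is stored under the nominal visit or as unscheduled.
- **6.3.14.4 and 6.3.14.5:** base the toxicity-graded shift tables on the worst post-dose grade in each named interval, including repeats, re-checks and unscheduled values.

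The cost is SAP wording and derivation code; no new data are needed. The downside is somewhat higher abnormality counts in both arms, including some transient or spurious readings. The by-visit continuous summaries and the listings would still show readings that settled.
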